### **17.4.3 Numerical rating scores for leg pain at baseline, and at 18, 30, 42 and 54 weeks after randomisation**

#### **17.4.3.1 Derivation**

Numerical rating scores for leg pain at baseline can be found in patient questionnaire booklet 1. This is a continuous outcome that gives a numerical rating between 1 and 100 denoting the severity of the pain, where 0 and 100 denote “no pain” and “worst pain you can imagine” respectively. The MACRO variable name is NUMRATBI and takes a value between 1 and 100. The date that the patient questionnaire (booklet 1) has been completed is also required for this outcome; see section 17.4.1.1 for details on how to derive missing questionnaire completion dates.

#### **17.4.3.2 Analysis**

For this outcome see section 17.4.2.2 for analysis details. In addition to this, effect estimates, 95% CIs and a p-value at T18 should be reported.

### **17.4.4 Numerical rating scores for back pain at baseline, and at 18, 30, 42 and 54 weeks after randomisation**

#### **17.4.4.1 Derivation**

Numerical rating scores for back pain at baseline can be found in patient questionnaire booklet 1. This is a continuous outcome that gives a numerical rating between 1 and 100 denoting the severity of the pain, where 0 and 100 denote “no pain” and “worst pain you can

imagine”, respectively. The MACRO variable name is NUMRATAI and takes values between 1 and 100. The date that the patient questionnaire (booklet 1) has been completed is also required for this outcome; see section 17.4.1.1 for details on how to derive missing questionnaire completion dates.

#### 17.4.4.2 Analysis

For this outcome see section 17.4.2.2 for analysis details. In addition to this, effect estimates, 95% CIs and a p-value at T18 should be reported.

### 17.4.5 Likert Scale to assess patient treatment satisfaction at 54 weeks after randomisation

#### 17.4.5.1 Derivation

Scores from the Likert Scale can be found from questions 6 and 7 of the COMI. The COMI score is calculated by recoding responses as in Table 17.4.5.1(a) and taking the average of both items. This score should only be calculated if all items are present.

**Table 17.4.5.1(a)**

Item no (MACRO variable)	Recoding
COMI6C	1= Very satisfied 2 = Somewhat satisfied 3 = Neither satisfied nor dissatisfied 4 = Somewhat dissatisfied 5 = Very dissatisfied
COMI7C	1= Very satisfied 2 = Somewhat satisfied 3 = Neither satisfied nor dissatisfied 4 = Somewhat dissatisfied 5 = Very dissatisfied

#### 17.4.5.2 Analysis

Patient treatment satisfaction scores at 54 weeks will be compared between groups using the Mann-Whitney U test. A blind review of the data was undertaken and the distribution of the Likert score at 54 weeks was found to be non-normal. The mean difference (along with a 95% confidence interval), test-statistic and p-value will be presented. Summary statistics (mean, SD and range) will also be presented for each treatment group.

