### 9.2 Method of Randomisation

Randomisation will be stratified by study centre. Randomisation schedules will be generated for each stratum using block randomisation, with random variable block length.

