## 9.6 Analysis Plan

The primary outcome (ODQ score at 18 weeks post-randomisation) will be compared between groups using a linear regression model, adjusted for the stratification variable centre, baseline ODQ score, and possibly other (specified in advance) variables considered to be potential confounders. Analysis of secondary outcomes will use similar methods, with logistic regression analyses used where appropriate. The intention to treat principle will be applied as far as is practically possible. The analysis set for the primary outcome will include all participants with an ODQ score at 18 weeks. Reasons for missing primary outcome data will be assessed, blind to treatment allocation, as to whether they are informative of likely outcome. Participants with non-informative reasons for missingness will be excluded from the primary analysis set. Sensitivity analyses will be carried out using multiple imputation to assess the robustness of the analysis to missing primary outcome data.

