## 5. Statement of Compliance

This Statistical Analysis Plan (SAP) provides a detailed and comprehensive description of the pre-planned **final** analyses for the study “NErve Root Block VErSUS Surgery (NERVES)”. The planned statistical analyses described within this document are compliant with those specified in brief within the NERVES protocol version 7.0 dated 25/10/2017.

This study is carried out in accordance with the World Medical Association Declaration of Helsinki (1964) and the Tokyo (1975), Venice (1983), Hong Kong (1989) and South Africa (1996) amendments and will be conducted in compliance with the protocol, Clinical Trials Research Centre (CTRC) Clinical Trials Unit (CTU) Standard Operating Procedures (SOPs) and EU Directive 2001/20/EC, transposed into UK law as the UK Statutory Instrument 2004 No 1031: Medicines for Human Use (Clinical Trials) Regulations 2004.

These planned analyses will be performed by the trial statistician.

This study is a clinical trial of a medicinal product and is registered on the European Union Drug Regulating Authorities Clinical Trials (EudraCT) database. The statistical analysis plan has been developed to support the posting of results on the EudraCT system. This is a regulatory requirement which should be fulfilled within 6 months after the end of the study as defined within the clinical trial protocol.

The results of the final analysis described within this statistical analysis plan will be contained within a statistical analysis report. This report will be used as the basis of the primary research publications according to the study publication plan.

All analyses are performed with standard statistical software (SAS version 9.3 or later). The finalised analysis datasets, programs and outputs will be archived following Good Clinical Practice guidelines and SOP TM021 Archiving procedure in CTRC. The testing and validation of the statistical analysis programs will be performed following SOP ST001: Statistical Analysis and Reporting.

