### 8.10. Method of assignment to treatment

Full details of the randomisation procedure can be found in section 6.3 and 9.2 in the protocol. Participants are randomised to treatment groups in a ratio of 1:1 using an online web randomisation system. Randomisation will be stratified by centre.

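### Treatment satisfaction is compared by a Mann-Whitney test that ignores centre, the randomisation stratum; the test stays valid but is mildly conservative if centres differ

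*SAP*

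**What the plan says.** **Randomisation.** Protocol 9.2: "Randomisation will be stratified by study centre", and "Randomisation schedules will be generated for each stratum using block randomisation, with random variable block length". SAP 8.10 repeats the factor: "Randomisation will be stratified by centre".

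**Protocol analysis.** Section 9.6 specifies for the primary outcome a "linear regression model, adjusted for the stratification variable centre, baseline ODQ score", with room for other prespecified covariates. It then says: "Analysis of secondary outcomes will use similar methods, with logistic regression analyses used where appropriate". Centre is not named again for the secondary outcomes.

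**SAP analysis.** Section 5 claims agreement with the protocol: "The planned statistical analyses described within this document are compliant with those specified in brief within the NERVES protocol version 7.0". Centre is in the primary model (17.4.1.2). It is a random effect in the repeated-measures model for later ODQ (17.4.2.2) and, by cross-reference, for leg pain, back pain, Roland-Morris and COMI (17.4.3.2, 17.4.4.2, 17.4.6.2, 17.4.7.2).

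**Satisfaction.** Section 17.4.5.2: "Patient treatment satisfaction scores at 54 weeks will be compared between groups using the Mann-Whitney U test". The reason given is: "A blind review of the data was undertaken and the distribution of the Likert score at 54 weeks was found to be non-normal". A mean difference with a 95% confidence interval is to accompany the test. The SAP change log records that the test replaced a planned t-test.

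**Work status.** Section 17.4.8.2 uses a plain chi-square test with a relative risk, also without centre.

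**The concern.** Blocking within centre makes the two arms nearly equal in size in every centre. Differences between centres then largely cancel out of the treatment comparison. A test that ignores centre still counts those differences as random error, so it overstates the variance of its own statistic. The p-value tends to be too large, the true type I error falls below the 5% stated in SAP section 12, and power is lost.

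Non-normality is a good reason to use ranks. It is not a reason to leave out the stratum, because a stratified rank test is equally free of the normality assumption.

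The protocol leaves room for centres to differ. Injection technique and repeat injections follow local policy (7.2), surgery follows local protocols (7.3), and variation in the interventions is expected (7.5.2). Whether this carries through to satisfaction is not known from the documents.

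**Working it through.** **1. The plan's own figures.** No sample size or power is stated for satisfaction, so only the ODQ calculation can be reproduced.

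- Difference 10, SD 20, two-sided 5%, 90% power: n per arm = 2 × (1.96 + 1.2816)² × 20² / 10² = 84.1, rounded up to 85. The t-based value is 85.03, rounded up to 86, which gives the stated 172.
- Revised with correlation 0.49: 86 × (1 − 0.49²) = 65.4, rounded up to 66 per group.
- With 10% loss: 66 / 0.9 = 73.3, rounded up to 74 per group, 148 in total.

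The stated figures reproduce.

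**2. Expected direction.** Let ICC be the between-centre share of variance. With perfect balance within centres, the true variance of the comparison is about (1 − ICC) times what an unstratified test assumes. Its type I error is then about 2 × Φ(−1.96 / √(1 − ICC)).

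- ICC 0.05: 1.96 / √0.95 = 2.011, giving 4.4%
- ICC 0.10: 1.96 / √0.90 = 2.066, giving 3.9%
- ICC 0.20: 1.96 / √0.80 = 2.191, giving 2.8%

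This is an idealised guide. Few centres, incomplete blocks, missing data and a coarse score should all soften it.

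**3. Simulation.** From the documents: 148 patients, 1:1 blocked allocation within centre, 10% missing, two-sided 5%, and a score that is the mean of two 5-level items. Seven centres come from protocol 9.4, which describes the original 200-patient plan.

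Assumed: blocks of 2 or 4; centre sizes of 40 and six of 18; a skewed score cut from a latent normal variable; a treatment shift of 0.5 latent SD; and the ICC values on the latent scale. There were 4,000 trials per cell.

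| ICC | Type I error: Mann-Whitney | Type I error: van Elteren | Power: Mann-Whitney | Power: van Elteren |
|---|---|---|---|---|
| 0 | 5.1% | 5.1% | 82.3% | 81.3% |
| 0.05 | 4.1% | 4.4% | 82.8% | 83.2% |
| 0.10 | 4.2% | 4.8% | 83.5% | 84.4% |
| 0.20 | 3.3% | 4.9% | 83.9% | 87.8% |
| 0.30 | 2.8% | 5.2% | 85.8% | 92.0% |

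The Monte Carlo standard error is about √(0.05 × 0.95 / 4000) = 0.3 points for type I error and √(0.83 × 0.17 / 4000) = 0.6 points for power. The shift is fixed relative to the total SD, so power should be compared within a row.

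**4. Other centre layouts.** With 11 centres (assumed: one of 36, eight of 11, two of 12), the results at ICC 0.20 are type I error 3.3% against 5.0% and power 83.8% against 87.0%. At ICC 0.05 the plain test is slightly ahead (82.2% against 81.5%). At ICC 0 it leads by 82.4% to 80.1%.

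A separate run of 6,000 trials per setting, with 132 evaluable patients (one centre of 36, six of 16), agrees. At 10%, type I error is 4.4% against 5.2% and power 82% against 84%. At 20%, the figures are 3.2% against 5.2% and 83% against 87%.

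**5. Break-even.** Linear interpolation gives the ICC at which stratifying starts to gain power. With 7 centres it is 0.05 × 1.0 / (1.0 + 0.4) = 0.04. With 11 it is 0.05 + 0.05 × 0.7 / (0.7 + 0.5) = 0.08. Both rest on differences of about a point, so they are rough.

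**The case against.** The strongest case for leaving the plan alone is that the plain test is valid and errs on the safe side. It affects a secondary outcome with no stated power, and no trial decision hangs on it. Which test has more power depends on a between-centre variance that neither document gives. Below an ICC of roughly 0.04 to 0.08 the plain test does as well or slightly better. All of this stands, and it sets the weight of the point.

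Four stronger readings are tempting, and the documents do not support them.

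- *The SAP breaches the protocol.* A reader might infer this from "Analysis of secondary outcomes will use similar methods, with logistic regression analyses used where appropriate" together with the SAP's compliance statement. Protocol 9.6 names centre only for the primary model. The similarity cannot be literal in any case, since satisfaction has no baseline measurement (Protocol Table 3). Centre adjustment is the natural reading, and the SAP follows it for the other patient-reported scores, but it is not an explicit requirement.
- *Centre was lost when the t-test was replaced.* The change log describes the earlier plan only as a t-test and mentions no centre term. Nothing shows that centre was ever included.
- *Satisfaction is the only lapse.* The work-status comparison also omits centre. The SAP models its repeated scales and uses simple two-group tests for these two outcomes.
- *The result would be biased or its error rate inflated.* In the simulations, type I error for the plain test is close to 5% with no centre effect and lower when centres differ.

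**Conclusion.** The point holds as a modest inefficiency. The satisfaction test ignores a factor that the trial randomises by and that the SAP uses for its other patient-reported scores. No reason is given for the omission. The test is valid, and conservative if centres differ. Type I error is about 4% at an ICC of 0.05 to 0.10 and 3.3% at 0.20. In the seven-centre simulation the power loss is about 1 point or less up to 0.10 (2 points at 0.10 in the 132-patient run) and about 4 points at 0.20.

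These sizes rest on assumed ICCs, centre sizes, block lengths and treatment shift. The documents give no centre-level satisfaction data, and the list of participating centres is a separate document. No simulation was run for work status; there the gap is established from the text only.

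**What to change.** In SAP 17.4.5.2, name one centre-stratified method and report an effect measure that belongs to it. Either:

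- the van Elteren test stratified by centre, with a centre-stratified effect estimate and 95% CI; or
- a proportional-odds model with treatment and centre, reporting the adjusted odds ratio and 95% CI.

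These are not interchangeable. The first is a stratified rank test. The second estimates a conditional odds ratio under a proportional-odds assumption, and a score with up to nine levels (1 to 5 in half steps) may leave sparse cells. Changing the test alone would leave the planned mean difference and its interval unadjusted, so the p-value and interval would still not match.

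State a rule for pooling small centres, fixed before outcomes are joined to allocation. Apply the same stratification to work status in 17.4.8.2, for example by a Cochran-Mantel-Haenszel test with a centre-stratified relative risk and 95% CI. If the plain tests are kept, say why centre is left out.

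The cost is a few SAP sentences, small programming changes and the pooling rule. The statistical downside for satisfaction is about 1 to 2 points of power if centres do not differ.

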#### **17.4.6 Modified Roland-Morris outcome score for sciatica at baseline, and at 18, 30, 42 and 54 weeks after randomisation**

##### **17.4.6.1 Derivation**

Modified Roland-Morris scores can be found in patient questionnaire booklet 1. The score is obtained by adding up the number of items the patient has ticked. Scores can vary between 0 and 24 and greater levels of disability are reflected by higher scores [11]. The MACRO variable names for each of the statements on the form are MODRM01C, MODRM02C, MODRM03C, MODRM04C, MODRM05C, MODRM06C, MODRM07C, MODRM08C, MODRM09C, MODRM10C, MODRM11C, MODRM12C, MODRM13C, MODRM14C, MODRM15C, MODRM16C, MODRM17C, MODRM18C, MODRM19C, MODRM20C, MODRM21C, MODRM25C, MODRM26C and MODRM27C. Any of the variables selected by the patient should be recoded to “1” and all variables not selected recoded to “0”. The date that the patient questionnaire (booklet 1) has been completed is also required for this outcome; see section 17.4.1.1 for details on how to derive missing questionnaire completion dates.

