### **Participants not attending Visits (Weeks 18 and 54)**

It is important that the patient attends the Week 18 visit as this is when the primary outcome data for the trial is collected. The participant should be contacted as per trust policy to urge them to attend.

If these attempts fail, the trial site should email CTRC to seek approval to post out the Patient Questionnaire Booklet 1, explaining circumstances. CTRC will indicate whether the Patient Questionnaire Booklet 1 can be posted to the participant if the participant does not attend their visit and all attempts of contact have failed.

Visits should be arranged initially for the first two weeks of the visit window as this gives time for the questionnaire booklet to be sent out by post and completed by participant within visit window in cases of non-attendance. The questionnaire booklet should be accompanied by the standard covering letter and a pre-paid envelope to enable the patient to return the booklet directly to CTRC.

If a visit does not take place, the site should also telephone the patient to try and retrieve as much Form 4: Follow-up Visits information as possible over the telephone (such as adverse event information, date returning to work) and record the information obtained in the patients notes as source data. This telephone call should be carried out by the person who was due to conduct the visit. Information obtained and recorded within source data should then be transcribed onto Form 4 and returned to CTRC. If information is unable to be obtained by

telephone, Form 4 should still be returned to CTRC notifying a non-attendance (Did Not Attend - DNA).

For the Week 18 visit **only**, a telephone call may be used to collect primary outcome data (**Part 1** of Patient Questionnaire Booklet 1 (ODQ)) in exceptional circumstances, with agreement from the CTRC. A telephone call must only be used to collect this data if all attempts to urge the patient to attend their Week 18 visit have failed, and the patient has not returned the Patient Questionnaire Booklet 1. Trial sites should contact the CTRC in this scenario to ensure all options for patient attendance at the Week 18 visit have been exhausted and to receive a script for the telephone call.

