#### **17.4.7 Core Outcome Measures Index (COMI) at baseline, and at 18, 30, 42 and 54 weeks after randomisation**

##### **17.4.7.1 Derivation**

Core Outcome Measures Index scores can be found in patient questionnaire booklet 1 (Questions 1-5). Pain intensity, function and symptom-specific and general well-being are measured using a 1-5 point Likert scale. Disability measurements for social life and work are measured in days of work incapacity/restricted activity over the past 4 weeks and could range from 0 to 28. The COMI score is calculated by recoding responses as in Table 17.4.7.1(a) and taking the average of all items. COMI scores should only be calculated if all items are present.

The date that the patient questionnaire (booklet 1) has been completed is also required for this outcome; see section 17.4.1.1 for details on how to derive missing questionnaire completion dates.

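### A skipped Roland-Morris page in a returned booklet scores 0 of 24, the same as full recovery; separately, the stated 1–100 pain range leaves out its own no-pain value of 0

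*SAP*

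**What the plan says.** **Roland-Morris.** SAP 17.4.6.1 defines the score as a count: "The score is obtained by adding up the number of items the patient has ticked". It lists the database variables and directs that a selected one becomes 1 "and all variables not selected recoded to" 0. On direction it says "Scores can vary between 0 and 24 and greater levels of disability are reflected by higher scores", so 0 is the best value. It does not mention a page with no marks.

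**Other multi-item scores.** Each has a completeness rule. The ODQ needs at least 8 of its 10 items (SAP 17.4.1.1). For the COMI, "COMI scores should only be calculated if all items are present" (SAP 17.4.7.1). The satisfaction score needs both of its items (SAP 17.4.5.1).

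**General provisions.** SAP 17.1 limits each analysis to participants whose outcome was observed and asks for documented reasons for exclusion. SAP 18 tabulates missing data for every secondary outcome.

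**Data routes.** Under Protocol 8.1, weeks 30 and 42 are postal, and the booklet goes from the patient straight to the trials unit. At week 18, in exceptional circumstances, "a telephone call may be used to collect primary outcome data", limited to the ODQ part of the booklet.

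**Pain.** SAP 17.4.3.1 describes leg pain as a "numerical rating between 1 and 100 denoting the severity of the pain, where 0 and 100 denote" no pain and the worst pain imaginable. SAP 17.4.4.1 repeats this for back pain and adds: "The MACRO variable name is NUMRATAI and takes values between 1 and 100".

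**The concern.** On a tick-list, an empty page has two meanings: either none of the statements applies today, or the respondent did not fill it in. The SAP gives both the same number, and it is the number for no disability. An unanswered page is then neither excluded nor counted as missing. It becomes a record of complete recovery, lowers that arm's mean, and drops out of the missing-data table in SAP 18. If skipped pages are more common in one arm, or come from more disabled patients in one arm, the treatment difference on this outcome is biased.

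Later steps are unlikely to catch it. The independent re-programming in SAP 21 covers the primary and safety analyses only. Multiple imputation in SAP 18 covers the primary outcome only.

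The pain point is a different kind of problem. The derivation sections contradict themselves about whether 0 is a valid value. If a range check were programmed to the stated range, pain-free answers would be flagged.

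**Working it through.** **1. Reproduce the stated range.** SAP 17.4.6.1 lists variables 01 to 21 (21 items) and 25, 26 and 27 (3 items). 21 + 3 = 24, which agrees with the stated range of 0 to 24.

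**2. Apply the rule literally** (selected = 1, not selected = 0, then sum):

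- page skipped: 24 × 0 = 0
- page read, nothing applies: 24 × 0 = 0
- every statement ticked: 24 × 1 = 24

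The first two cannot be told apart.

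**3. Which records are exposed?**

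- *Booklet not returned.* The outcome was not observed, so SAP 17.1 excludes it.
- *Week-18 telephone ODQ only.* Roland-Morris was not administered. On a fair reading SAP 17.1 excludes it too, though no text says so for this score.
- *Booklet returned, Roland-Morris page empty.* SAP 17.1 does not say whether this is observed, and SAP 17.4.6.1 instructs a 0. This is the gap.

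In clinic, staff should check booklets before the patient leaves, where possible (Protocol 8.1, note under Table 2). The postal booklets have no such check. The telephone prompt at weeks 30 and 42 is for non-response, not for a skipped page in a returned booklet.

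**4. Size, on assumed inputs.** Let *b* be the share of an arm's booklets at a visit with the page skipped, and *m* the mean those patients would have scored. Each such score falls from its true value to 0, so

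shift in arm mean = −*b* × *m*.

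Neither *b* nor *m* is in the documents. Over an assumed range:

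| *m* | *b* = 2% | *b* = 5% | *b* = 10% |
|---|---|---|---|
| 6 | −0.12 | −0.30 | −0.60 |
| 10 | −0.20 | −0.50 | −1.00 |
| 14 | −0.28 | −0.70 | −1.40 |

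For the difference between arms A and B:

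bias = −(*b*A × *m*A − *b*B × *m*B).

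With *m* = 10 and *b* = 5% in both arms: −(0.50 − 0.50) = 0. With *m* = 10 in both, *b*A = 5% and *b*B = 2%: −(0.50 − 0.20) = −0.30 points. These are shifts in raw means at one visit. The planned model (SAP 17.4.2.2, applied through 17.4.6.2) pools all follow-up visits, so a shift confined to weeks 30 and 42 would generally be diluted in its estimates.

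**5. Pain range.** A value of 0 fails 1 ≤ *v* ≤ 100 and passes 0 ≤ *v* ≤ 100. Values 1 and 100 pass both. The SAP's no-pain anchor is therefore outside the SAP's own range.

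**The case against.** **SAP 17.1 already restricts analyses to observed outcomes.** Read with it, the recode to 0 concerns a completed questionnaire. This stands for unreturned booklets and, fairly read, for telephone-only week-18 records. A reader might infer that the telephone fallback manufactures perfect Roland-Morris scores; the documents do not support that. The objection does not reach the skipped page in a returned booklet, because no text defines it as unobserved.

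**The comparison with ODQ and COMI is loose.** Those items each require a choice, so a blank is visible. On a tick-list an unticked statement is an answer, and a rule of the 8-of-10 kind cannot be carried over. This is right, and it limits the remedy: a skipped page in an otherwise completed booklet cannot be identified with certainty.

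**Booklets are checked.** Clinic checks (Protocol 8.1) and central checks with queries (Protocol 13.4) reduce the problem. They protect the postal visits less, and a central check cannot recognise an unticked box as missing. No blank-page rate is given, so the problem may be small.

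**The pain wording is a slip.** Very likely. The sentence that gives 1 to 100 also defines 0, and Protocol 13.4 queries unusual values rather than deleting them. A reader might infer that pain-free answers are lost. If 15% of an arm scored 0 and the rest averaged 35 (both assumed), discarding the zeros would move the mean from 0.85 × 35 = 29.75 to 35. No rule in either document discards, recodes or sets zeros to missing, so that shift is not a consequence of the plan as written.

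**Conclusion.** The Roland-Morris point holds in a limited form. As written, SAP 17.4.6.1 gives a wrong value to a skipped page in a returned booklet, and nothing elsewhere in the SAP overrides it. The main exposure is at weeks 30 and 42.

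The effect is confined to a secondary outcome; the primary ODQ analysis is untouched. Its size cannot be found from the documents. The 0.12 to 1.4 points per arm rest wholly on assumed blank rates and true scores, and most of the shift cancels in the treatment contrast if those are similar between arms. The documents give no reason to expect them to differ. It would also be wrong to say that response rates are distorted: SAP 17.4.2.2 and 17.4.6.2 compare mean scores.

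The pain point holds as an internal contradiction in SAP 17.4.3.1 and 17.4.4.1, also on secondary outcomes. It is not a stated rule that loses data.

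Both are minor and worth correcting because the correction is cheap.

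**What to change.** **SAP 17.4.6.1.** Add that the score is missing when

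- Roland-Morris was not administered (telephone ODQ only), or
- no statement is ticked and the adjoining booklet sections are also unanswered.

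For no-tick pages in otherwise completed booklets:

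- keep 0 in the main analysis, since it may be a true answer;
- report their number by arm and visit;
- flag those inconsistent with the same visit's ODQ, with the criterion fixed beforehand (one option is an ODQ above 20%, the top of the minimal-disability band in SAP Table 17.4.1.1(b));
- run one sensitivity analysis with all no-tick pages set to missing.

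The main analysis will still score an isolated skipped page as 0. The count, the flag and the sensitivity run show whether that matters. The drawback of the sensitivity run is that it also drops genuine zeros, so it should be read beside the main result and not in place of it.

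**SAP 17.4.3.1 and 17.4.4.1.** Change 1–100 to 0–100 in both places in each section, and confirm that the database range checks accept 0.

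**Cost.** A few sentences, a small change to the derivation code, one short table and one extra model run. No new data are needed.
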